## 1.0 Objectives

### 1.1 Study Objectives

In this study, we will test the central hypothesis that postmenopausal women will demonstrate increased oxygen extraction in active leg muscle during leg cycling exercise while receiving an infusion of Esmolol, a fast-acting  $\beta_1$  selective antagonist, when compared to premenopausal women.  $\beta_1$  selective antagonists (or “ $\beta_1$  blockers”) are used to lower heart rate and improve  $O_2$  supply-to-demand balance in patients with coronary artery disease. By using esmolol to attenuate the central sympathetic response to exercise (increased heart rate and cardiac output) we can examine peripheral mechanisms of  $O_2$  delivery. The current project will evaluate how older postmenopausal women adjust active muscle  $O_2$  supply to an acute reduction in systemic  $O_2$  delivery during large muscle dynamic exercise when compared to younger premenopausal women.

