## 2.2 Previous Data

Because of its rapid onset and offset, Esmolol is used commonly in anesthesia and critical care to treat tachycardia. Our dose-finding studies indicated that infusing of ~125 mg of Esmolol (range 90 to 162 mg) acutely blocks beta-1 adrenergic receptors ( $\beta$ 1ARs) in healthy young men and women.  $\beta$ 1ARs remain blocked in these subjects if a maintenance infusion of Esmolol continues. When the infusion ends, the  $\beta$ 1ARs return to baseline within 45 minutes.

There are minimal published data using Esmolol in the context of exercise physiology experiments. The [name] lab recently utilized the rapidly acting  $\beta$ 1 selective antagonist esmolol to transiently reduce exercise heart rate in a mixed (age and sex) sample of healthy adults. Larger reductions in near infrared spectroscopy (NIRS)-derived oxyhemoglobin/myoglobin O2 saturation (an index of O2 extraction) were observed within the exercising leg muscles (vastus lateralis and medial gastrocnemius) of these subjects during esmolol (vs. saline) infusion. These findings provide strong evidence of the dynamic coupling that exists between systemic O2 delivery and active muscle O2 extraction during submaximal exercise in humans.

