All measurements (HR, BP, cardiac output, oxygen consumption and NIRS) will be continue to be collected throughout the exercise protocol (some continuously, others intermittently). Once these measurements have stabilized (i.e., approximately 10 minutes into the maintenance infusion), the subject will be asked to squeeze the handgrip device (constant tension) at 40% of the force they developed during the maximum grip testing for 1-2 minutes. Once all measurements have returned to baseline, the subjects will then begin the cycling exercise protocol. Subjects will be asked to pedal for 2 minutes at a very light intensity, followed immediately by 5 minutes at a light intensity, and 5 minutes of cycling at a moderate intensity. Finally, the subject will continue cycling at the same moderate intensity for 1 to 2 minutes while simultaneously squeezing a handgrip device at 40% of their maximal effort. The subject will then rest for 45 mins, after which they will repeat the exercise protocol. Immediately following the second exercise bout, cuffs will be placed on the upper arm and on the upper thigh of the limbs with the NIRS probes attached. The cuffs will then be inflated to ~250 mmHg until the limbs have been completely deoxygenated (~5 minutes as determined by NIRS).

After the recovery period, most instrumentation will be removed (except for the blood pressure cuffs and EKG). The subject will then sit up slowly as we monitor their BP and HR, and offer them juice and crackers. Once the subject's BP and HR have returned to baseline levels, we will remove the remaining monitoring equipment and the subject may leave. There is no need to send subjects home with a heart rate monitor after the study because the effects of Esmolol are very short (9-minute half-life).

Listed below are all the parameters that will be measured. The risks of each procedure are listed in Section 11.0.

1. **Oxygen consumption (VO2)**: Pulmonary oxygen consumption will be measured using a COSMED Quark breath-by-breath system. A silicone mask will be placed over the subject's nose and mouth to measure breather frequency and volume in addition to the expired gas content.

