### 7.4 Test Article(s) (Study Drug(s) and/or Study Device(s))

Esmolol hydrochloride will be handled following the Institution's Standard Operating Procedures for Clinical Research Section III, PM 306. Esmolol will be tracked using an accountability record, and dispensed by a physician, pharmacist, PA, or CRNP. The receipt, storage, dispensing and return/destruction will follow the Institution's Standard Operating Procedures for Clinical Research.

- **Description**

Esmolol hydrochloride (2500 mg in 250 ml normal saline) will be purchased from McKesson in pre-mixed bags. The placebo will be a 250 ml, 500 ml, or 1000 ml bag of normal saline.

- **Treatment Regimen**

The route of administration of Esmolol in our study is the same as in clinical care (IV pump). The loading dose will be 0.5 mg/kg fat free mass/min administered over the first 3 minutes, followed by a maintenance dose of 0.25 mg/kg fat free mass/min for the remainder of the protocol (maximum of 60 minutes).

- **Method for Assigning Subject to Treatment Groups**

This study uses a crossover design so all subjects will complete both treatments in random order. Subjects will be randomized to one of two treatment sequences using an equal allocation ratio of 1:1. The two treatment sequences to which subjects will be randomized are 1) Esmolol infusion first and saline infusion second and 2) saline infusion first and Esmolol infusion second. The CRC nurses will generate the randomization that will use variable size, random permuted blocks with block size 2 and 4. CRC staff will maintain the randomization list until data collection has been completed to keep the research staff blinded.

- **Subject Compliance Monitoring**

Not applicable.

- **Blinding of the Test Article**

This study is single blind because the subjects, data collectors, and data analysts will not be aware of the treatment. For safety reasons, the CRC nurse will not be blinded. Additionally, once the Esmolol/saline infusion pump is programmed by the research nurse, an opaque bag will be placed over the fluid bag so that the participant and all investigators in the room remain blinded to the treatment order.

- **Receiving, Storage, Dispensing and Return**

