### **9.6 Frequency of review of cumulative data**

Subject data are analyzed by [name] graduate student within two weeks of each study visit. Summary data are reviewed at least once per month to ensure the protocol and measurements are appropriate. Safety is

constantly monitored during the trials and any concerns are brought to the attention of the PI immediately. We do not wait for a cumulative review to assess safety.

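### The stated blinding of data collectors and analysts is unlikely to hold, because heart rate is recorded with NIRS for both infusions in one visit and no fixed rules govern how SmO2 is derived

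*Combined protocol and SAP*

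**What the plan says.** Section 7.4 states that "the subjects, data collectors, and data analysts will not be aware of the treatment", and Section 7.1 says the same of treatment order. The one named exception is that "For safety reasons, the CRC nurse will not be blinded". The measures described are:

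- a cover: "an opaque bag will be placed over the fluid bag so that the participant and all investigators in the room remain blinded" (7.4);
- the same infusion volume and rate in both trials (7.1);
- a withheld list: "CRC staff will maintain the randomization list until data collection has been completed to keep the research staff blinded" (7.4);
- nurses kept out of data analysis (7.1).

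Section 1.1 explains that esmolol is used to blunt the exercise rise in heart rate and cardiac output. Section 2.2 reports the group's earlier use of "esmolol to transiently reduce exercise heart rate in a mixed (age and sex) sample of healthy adults", and Section 2.3 puts the cardiac effect within 5 minutes. In Section 7.2.3 both infusions fall in visit 3, with the exercise protocol repeated after 45 minutes of rest, and "All measurements (HR, BP, cardiac output, oxygen consumption and NIRS) will be continue to be collected throughout the exercise protocol".

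Section 9.1 makes the principal investigator (PI) solely responsible for collecting and verifying data. On analysis, Section 9.6 names a graduate student within two weeks of each visit, while Section 9.7 names the PI within one week. Both add a regular look: "Summary data are reviewed at least once per month to ensure the protocol and measurements are appropriate".

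**The concern.** The safeguards act on the label, whereas treatment can be inferred from the response. Each woman performs the same protocol twice on one day, once with a drug chosen to lower heart rate, and the team must judge when the measurements have stabilised and returned to baseline before moving on. Anyone who sees both heart-rate records has good grounds to guess the order.

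This matters because NIRS gives an instrument reading, but the percentage change in SmO2 is a derived quantity. Section 1.2 refers only to the active leg muscle, while Section 7.2.3 (item 7) records thigh and calf and lists tissue saturation index, oxy-, deoxy- and total haemoglobin. No text fixes the site, signal, baseline window, steady-state window, artefact rule or use of the occlusion calibration. Age group is evident to staff in the room, no step hides it from the NIRS reader, and Section 1.2 states a directional prediction. At stake are the within-group esmolol-saline effect and, on a narrower route, the primary comparison between age groups.

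**Working it through.** **The plan's own figure.** Inputs from Section 8.2: difference 5.8 points, SD 4.78, two-sided 5%, 80% power. Normal approximation: n = 2 × (1.960 + 0.842)² × 4.78² / 5.8² = 10.7, so 11 per group, as stated. With the noncentral t, power is 77.2% at 11 and 84.3% at the planned 13. Nothing below depends on a change of sample size.

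**Can treatment be inferred?** The documents give neither the size nor the SD of the heart-rate fall, so both are assumed here. If an observer calls the bout with the lower heart rate esmolol, P(correct) = Φ(fall / SD of the within-subject difference), against 50% by chance:

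| Assumed fall (beats/min) | SD 10 | SD 5 |
|---|---|---|
| 5 | 69% | 84% |
| 10 | 84% | 98% |
| 15 | 93% | 99.9% |
| 20 | 98% | nearly 100% |

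**Who could act on it?** Sections 9.1 and 9.7 together make the PI both collector and analyst. Section 9.6 gives analysis to a graduate student, who is not said to be in the room. Under neither version is the analyst separated from the haemodynamic data.

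**Which comparison is exposed?** Let data reduction add b_O to the esmolol-saline difference in older women and b_Y in younger women. The observed group contrast is then (μ_O + b_O) − (μ_Y + b_Y) = (μ_O − μ_Y) + (b_O − b_Y). If b_O = b_Y, the bias cancels in the primary contrast but stays in each within-group effect. The primary test is affected only by b_O − b_Y.

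**What would a differential shift do?** With 13 per group and SD 4.78, the standard error is 4.78 × √(2/13) = 1.875, with 24 degrees of freedom. The noncentrality parameter is shift / 1.875. Two-sided rejection probability when there is no true difference:

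| Assumed b_O − b_Y (points) | Share of 5.8 | Noncentrality | Rejection probability |
|---|---|---|---|
| 0.5 | 9% | 0.27 | 5.8% |
| 1 | 17% | 0.53 | 8.1% |
| 1.5 | 26% | 0.80 | 12.0% |
| 2 | 34% | 1.07 | 17.6% |

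A shift against the prediction costs power instead: with a true difference of 5.8, power falls from 84.3% to 69.0% for 1 point and 49.4% for 2 points.

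**The case against.** Some loss of masking is inherent when the drug's intended effect is itself measured and watched for safety. The study calls itself single-blind and exploratory, order is randomised, and the list is withheld until data collection ends. That is fair, and it argues for stating the limit rather than for faulting the design.

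The route to the primary test is also narrow: an analyst would have to treat the two bouts differently, and do so differently by age. This stands, and it is why the error rates above are conditional.

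The scope for discretion may be smaller than it looks. Exercise stages are timed (2, 5 and 5 minutes), and one occlusion after the second bout appears to serve both bouts, which makes calibration a weak route for favouring one infusion. Protocol diagrams that might show measurement times are not available to us. Even so, a stage length is not an averaging window, and the text gives no rule for site, signal or artefacts.

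A reader might infer that SmO2 is certainly being compared by treatment during recruitment. The documents do not say so. Sections 9.6 and 9.7 refer only to subject data and sit in the safety monitoring plan, and the monthly review is described as a check on the protocol and measurements. Inclusion of SmO2 is a natural reading, not a stated one. Section 9.2 does list interim data evaluation, however, and nothing restricts the review to safety or signal quality.

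Finally, removing heart rate does not fully mask the file. Section 2.2 reports larger falls in muscle saturation under esmolol, so the NIRS trace may itself suggest treatment. This stands and limits what coding can achieve.

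**Conclusion.** The claimed blinding of collectors and analysts is unlikely to hold, and the plan should not rely on it. A reader might go further and say that it cannot hold. Without a heart-rate effect size the documents do not support that, and the guessing rates rest on assumed falls and SDs. Nor would it be right to say that a bag cover and a withheld list are the sole safeguards: the matched infusion rate and the exclusion of nurses from analysis are also stated, though neither hides heart rate.

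The within-group esmolol-saline effect is exposed to any treatment-related bias in data reduction. The primary contrast is exposed only to a bias that differs by age group. The figures of 8%, 12% and 18% assume average differential shifts of 1, 1.5 and 2 points; they illustrate sensitivity and do not estimate this trial's error rate. The true shift is unknown and may be zero. The change is worth making because it is cheap and leaves visits and sample size untouched.

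**What to change.** In Sections 7.4 and 8.3:

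1. Set the SmO2 reduction rules in advance: muscle site, signal, baseline and exercise windows, artefact handling and use of the occlusion calibration.
2. Have existing staff export NIRS files under neutral subject and bout codes, without age group, heart rate, blood pressure or cardiac output. The CRC already keeps the list linking codes to identifiers (22.4), but the plan should name who does the export.
3. Lock the SmO2 values before merging them with haemodynamic data or the randomisation list.
4. State that staff in the room may infer treatment from heart rate, and that coding reduces this problem but may not remove it, because the NIRS trace can itself be suggestive.

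In Sections 9.6 and 9.7, reconcile who analyses subject data and within what time. Limit the monthly review to safety and signal quality, with no SmO2 comparison by treatment or age group until data collection is complete.

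The cost is wording and a small file-coding step. The downside is that quality checks combining heart rate with NIRS must wait until the NIRS values are locked.

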#### **7.4.1 Receipt of Test Article**

Esmolol hydrochloride will be purchased from McKesson.

#### **7.4.2 Storage**

Esmolol is stored at room temperature in a locked cabinet that is temperature-monitored in the CRC. A special thermometer that records high and low temperatures will monitor the temperature in the storage area. The thermometer is checked on a regular basis by staff in the lab. The CRC is locked when unoccupied.

#### **7.4.3 Preparation and Dispensing**

A CRC physician or CRNP will calculate the required esmolol dose, configure the IV pump settings and monitor the subject during infusion. A CRC nurse will perform a double check of the calculated esmolol dose and IV pump settings prior to infusion. The amount of Esmolol used for each study/participant will be recorded on the study protocol flow sheet.

#### **7.4.4 Return or Destruction of the Test Article**

Any Esmolol bags (empty or partially used) remaining after completion of a study visit will be disposed on site.

#### **7.4.5 Prior and Concomitant Therapy**

A list of prior and current medications will be obtained during the screening visit as part of the medical history. Subjects will be asked to withhold all over-the-counter medications (e.g. motrin, cold medicine) for 24 hours prior to each study and during the study procedures. ALL participants will review their prescribed medications, including beta-blockers, with one of the research nurses. This information will be shared with the CRC clinician who will then recommend which medications can be taken prior to the patient's scheduled study visit, and which ones should be withheld until after the study. All medications consumed by the participants will be written on the flow sheet.

## **8.0 Subject Numbers and Statistical Plan**

### **8.1 Number of Subjects**

We plan to enroll no more than 40 subjects (20 subjects per group) in this study. We plan to complete data collection on 13 young women (age 21-35) and 13 older postmenopausal women (age 55-70).

### **8.2 Sample size determination**

$\Delta\Delta SmO_2$  (difference between  $\% \Delta SmO_2$  during saline and esmolol trials) in response to moderate-intensity cycling exercise is our primary outcome. We do not have any pilot data pertaining to Esmolol infusion and exercise in postmenopausal women. However, using data from our recent publication, older adults ( $65.0 \pm 2.6$  years,  $n=3$ ) displayed a greater  $\Delta\Delta SmO_2$  compared to their young ( $25.4 \pm 1.9$  years,  $n=5$ ) counterparts ( $22.0 \pm 4.0$  % vs  $16.2$  %).

$\pm 4.0\%{^{20}}$ . Considering this prior data, we will consider the difference between the pre-to-post Esmolol change and the pre-to-post placebo change (i.e., delta delta) of 5.8% to be clinically relevant. Furthermore, we assume the variability (i.e., standard deviation) will be 4.78%, the standard deviation seen from this previous data. We also assume there will be no carryover effect. Given these assumptions, a sample size of 11 subjects per group will provide 80% power to detect a difference in the change in  $\% \Delta \text{SmO}_2$  between Esmolol and placebo, assuming a standard deviation of 4.78%, using a two-sided test having a significance level of 0.05. To account for differences in subject population and exercise protocol between that study and this protocol, we plan to complete data collection on 13 subjects per group to ensure sufficient power. However, we expect a small number of individuals may not complete the study. Therefore, we plan to enroll up to 20 subjects per group for a total of no more than 40 subjects so that 13 subjects per group may complete the study.

### **8.3 Statistical methods**

Changes in outcomes will be calculated per patient prior to analyses. The data will be analyzed using repeated measures ANOVA, to account for the crossover design, with appropriate contrasts constructed to test hypotheses of interest (e.g., premenopausal vs postmenopausal). Additionally, where applicable, ANOVA will be used to assess differences between the groups for continuous outcomes (e.g.,  $\Delta \% \Delta \text{SmO}_2$ ). As this is a relatively small-scale exploratory study, no corrections for multiple hypothesis testing will be employed.

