### 1.2 Primary Study Endpoints

The primary outcome variable is the difference in the change in skeletal muscle oxygenation (% $\Delta SmO_2$ ) in the active leg muscle from baseline during recumbent cycling exercise between saline and esmolol ( $\Delta\% \Delta SmO_2$ ). We predict that older women will have a greater  $\Delta\% \Delta SmO_2$  than premenopausal women during esmolol infusion.

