### 7.2.3 Visit 3 (Infusion)

[figure not shown]
The order of infusion will be randomized and "blinded" such that neither the subject nor the investigators will know what the infusion order is (only the nurses will know the order, for safety reasons).

As with the screening visit, the subject will be told to avoid alcohol, over the counter cold prep and NSAIDs, and strenuous exercise for 24 hours, and to eat a small meal 2-3 hours prior to coming to the laboratory. They will also be asked to refrain from items containing caffeine 12 hours prior to this visit. Women of childbearing potential (pre-menopausal) will take a urine pregnancy test to ensure they are not pregnant.

Then the subject will then lay on an exam bed for placement of EKG pads as well as NIRS devices (one on the forearm, one on the forehead, and two on the leg) and measurement of vital signs. A nurse will then insert a catheter into a vein of the subject's arm (visit 3 only). This catheter will enable us to infuse the drug (Esmolol or saline).

The subject will then be assisted onto the recumbent bike. The subject will be asked to squeeze a handgrip device as hard as they can with their hand. The maximum force they can exert (highest of 2 to 3 efforts) will be used to determine how hard they will squeeze this device later in the study (40% of this maximum value). A silicone face mask will be placed over the subject's nose and mouth to monitor their oxygen consumption and breathing frequency, and blood pressure devices will be placed over their arm (SunTech Tango) and finger (Finometer). After all instrumentation is in place, baseline measurements of heart rate, cardiac output, oxygen consumption, blood pressure, and NIRS will begin. After all instrumentation is in place baseline measurements of heart rate, cardiac output, oxygen consumption, blood pressure, and NIRS will begin.

A CRC clinician will join the research team immediately before it is time to start the infusion. The CRC clinician will be able to review the EKG results at that time if there are any concerns. The subject will then receive an infusion of Esmolol or saline. The Esmolol loading dose will be 0.5 mg/kg fat free mass/min administered over the first 3 minutes (loading dose), followed by a maintenance dose of 0.25 mg/kg fat free mass/min for the remainder of the protocol (maximum of 60 minutes).

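### The primary age comparison carries no baseline covariate; if each bout has its own resting SmO2, prespecifying the between-bout resting difference could gain precision at little cost, by an amount the documents do not fix.

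*Combined protocol and SAP*

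**What the plan says.** Section 1.2 defines the primary outcome as the difference in the change in SmO2 "in the active leg muscle from baseline during recumbent cycling exercise between saline and esmolol". Section 8.2 describes the same quantity as "the difference between the pre-to-post Esmolol change and the pre-to-post placebo change", which reads as one resting value per treatment.

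On analysis, section 8.3 says: "Changes in outcomes will be calculated per patient prior to analyses". It continues: "The data will be analyzed using repeated measures ANOVA, to account for the crossover design, with appropriate contrasts constructed to test hypotheses of interest". For the double change itself, "ANOVA will be used to assess differences between the groups for continuous outcomes". No covariate is named for either model.

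On the resting measurement, section 7.2.3 describes one set-up, ahead of the infusion: "After all instrumentation is in place, baseline measurements of heart rate, cardiac output, oxygen consumption, blood pressure, and NIRS will begin". For the second bout it says only: "The subject will then rest for 45 mins, after which they will repeat the exercise protocol". A second resting window is implied but not stated. The documents also do not say whether %ΔSmO2 is in absolute points or a percentage of baseline.

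**The concern.** Subtracting a resting value gives it a coefficient of exactly 1. In the double change, what is subtracted is the woman's esmolol-minus-saline difference in resting SmO2. If two resting readings in the same session differ mainly through measurement noise, the coefficient that minimises variance is below 1, and the plain change score is noisier than it need be.

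What is at stake is the precision of the primary contrast with 13 completers per age group. Age group is not randomised, so adjusting for resting SmO2 level would be questionable, because the level may differ by age. The within-woman difference is another matter. Infusion order is randomised 1:1 (section 7.4), so a pre-infusion resting difference between the esmolol and saline bouts has expectation zero in both age groups, provided there is no carryover.

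**Working it through.** **Inputs from section 8.2.** Difference 5.8 points, SD of the double change 4.78, two-sided alpha 0.05, stated n of 11 per group for 80% power, 13 completers per group planned, no carryover assumed.

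**The plan's own figure.** Normal approximation: n = 2 × (1.960 + 0.842)² × 4.78² / 5.8² = 10.7, so 11 per group, as stated. At n = 11 power is 81.2% (normal) or 77.2% (t). At n = 13 it is 87.2% (normal) or 84.3% (t, 24 df). The reference below is 84.3%.

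**Model.** Let dE and dB be a woman's esmolol-minus-saline differences in exercise and resting SmO2. Let r = SD(dB)/SD(dE), and let rho be their correlation within age group.

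- Plain double change, dE − dB: variance = SD(dE)² × (1 + r² − 2·rho·r).
- Adjusted for dB: residual variance = SD(dE)² × (1 − rho²).
- Variance ratio, adjusted to plain: (1 − rho²) / (1 + r² − 2·rho·r). At r = 1 this is (1 + rho)/2.
- The best coefficient on dB is rho/r. When rho = r it equals 1, the ratio is 1 and nothing is gained.

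The SD of the plain double change is held at 4.78 throughout. Adjusted power uses the noncentral t with 23 df and variance inflation 1 + 1/22 for estimating the slope.

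**Results at 13 per group.** The values of r and rho are assumptions.

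| r | rho | Variance ratio | Residual SD | Adjusted power |
|---|---|---|---|---|
| 1 | 0.3 | 0.91/1.40 = 0.65 | 3.85 | 94.9% |
| 1 | 0.5 | 0.75/1.00 = 0.75 | 4.14 | 91.7% |
| 1 | 0.7 | 0.51/0.60 = 0.85 | 4.41 | 88.1% |
| 0.75 | 0.3 | 0.82 | 4.32 | 89.3% |
| 0.75 | 0.5 | 0.92 | 4.59 | 85.4% |
| 0.75 | 0.7 | 0.995 | 4.77 | 82.7% |
| 0.5 | 0.3 | 0.91/0.95 = 0.96 | 4.68 | 84.1% |
| 0.5 | 0.5 | 0.75/0.75 = 1.00 | 4.78 | 82.6% |
| 0.5 | 0.7 | 0.51/0.55 = 0.93 | 4.60 | 85.3% |

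The worst case is 84.3% − 82.6% = 1.7 points. Simulation (20,000 runs) agrees: plain versus adjusted power is 84.3% versus 91.7% at r = 1, rho = 0.5, and 83.9% versus 82.2% at r = 0.5, rho = 0.5.

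**Check on bias.** A further simulation (20,000 runs, r = 1, rho = 0.5) added a 4-point bout-order shift to both resting and exercise SmO2, in older women only. The adjusted estimate averaged 5.82 against a true 5.8, and type I error was 5.0%. A bout-order shift therefore does no harm when order is randomised. Carryover of esmolol into the second resting value was not part of this check.

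**The case against.** The strongest objection is that the premise is inferred. Section 7.2.3 describes one baseline. If that single value served both bouts and the change were in points, it would cancel exactly in the double change and there would be nothing to adjust. If %ΔSmO2 is a percentage of baseline, the resting value is a divisor and the algebra above does not carry over. Cycling also starts well into the infusion, so the value subtracted might be an on-infusion one, whose noise a pre-infusion covariate need not share. All of this stands. Section 8.2's two pre-to-post changes make a resting value per bout the natural reading, but the plan must say so.

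Second, a reader might infer that adjustment would remove much of the resting noise. The documents do not support that. The larger gains need r = 1, which with the SD held at 4.78 implies an SD of within-woman resting differences of 4.78/√1.4 = 4.0, 4.78/√1.0 = 4.8 or 4.78/√0.6 = 6.2 points at rho 0.3, 0.5 or 0.7. Nothing in the documents supports values of that size. The exercise difference also contains variation between women in response to esmolol, which the pre-infusion resting difference does not, so r below 1 is plausible.

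Third, a reader might infer that the sample size is wrong or the age contrast biased. Neither follows. The 4.78 comes from earlier data on the same double change, so it should already contain resting noise. It may even be conservative: groups of 3 and 5 with SD 4.0 and means 5.8 apart have a total SD of √[(2×16 + 4×16 + (15/8)×5.8²)/7] = 4.77, so 4.78 appears to include the age difference. With SD 4.0, unadjusted power at 13 per group is already 94.4%, which leaves little to gain.

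Fourth, in women given esmolol first, the second resting value follows active treatment. The covariate then relies on the no-carryover assumption in section 8.2. The receptor recovery within 45 minutes described in section 2.2 comes from healthy young adults. If recovery differed by age, the covariate could differ by age group and adjustment could bias the contrast.

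**Conclusion.** The point holds as a cheap improvement in precision whose size is uncertain. The plan compares a plain double change with no baseline covariate. If each bout has its own resting value and the change is in absolute points, noise from both resting values enters at full weight.

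For rho between 0.3 and 0.7, adjustment brings a useful gain if the resting and exercise between-bout differences are equally variable, and practically none if the resting difference is half as variable. The loss is bounded at about 1.7 points of power.

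The conclusion rests on a pre-infusion resting value for each bout, randomised order and no carryover that depends on age. The unadjusted ANOVA remains a valid analysis. The undefined resting window and unit of change need settling whether or not the covariate is adopted. Priority is low to moderate.

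**What to change.** In section 8.3:

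1. Define the resting SmO2 for each bout as the mean over a stated window immediately before that bout's infusion starts.
2. State whether %ΔSmO2 is in absolute points or a percentage of baseline.
3. Add wording such as: *The primary comparison is an ANCOVA of the double change in SmO2 on age group, with the woman's esmolol-minus-saline difference in pre-infusion resting SmO2 as covariate. The unadjusted ANOVA is reported alongside.*
4. Specify that the covariate is neither her resting level, which may differ by age and would not remove the between-bout noise, nor an on-infusion value, which may itself respond to esmolol.

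The cost is a few sentences and one degree of freedom, plus reliance on the plan's existing no-carryover assumption for the second resting value. NIRS is already being recorded, so the only possible addition is marking a resting window before the second infusion. The choice should be fixed before treatment order is unblinded.
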